### Compound specific safety evaluation

[figure not shown]
Safety topics of interest, such as risks defined in the Safety Profiling Plan (SPP), Risk Management Plan (RMP) or topics of interest regarding signal detection or routine analysis are defined in the Program Case Retrieval Strategy (CRS).

The crude incidence and exposure-adjusted incidence rates for SPP risks will be summarized. In addition, listings will be provided presenting which subjects experienced which risk.

Important note: For the evaluation of SPP risks, primary and secondary system organ classes and preferred terms of the MedDRA dictionary will be considered, as defined in the Program CRS and RMP.

### **Clinical Trial Safety Disclosure**

(see [references](#))

If for a same patient, several consecutive AEs (irrespective of study treatment causality, seriousness and severity) occurred with the same SOC and PT:

- a single occurrence will be counted if there is  $\leq 1$  day gap between the end date of the preceding AE and the start date of the consecutive AE
- more than one occurrence will be counted if there is  $> 1$  day gap between the end date of the preceding AE and the start date of the consecutive AE

[figure not shown]
For occurrence, the presence of at least one SAE / SAE suspected to be related to study treatment / non SAE has to be checked in a block e.g., among AE's in a  $\leq 1$  day gap block, if at least one SAE is occurring, then one occurrence is calculated for that SAE.

[figure not shown]
The number of deaths resulting from SAEs suspected to be related to study treatment and SAEs irrespective of study treatment relationship will be provided by SOC and PT.

#### **2.7.2 Injection reactions**

Injection reactions will be summarized by type of injection reaction (overall, local and systemic), by grading, and by visit.

#### **2.7.3 Laboratory data**

The summary of laboratory evaluations will be presented for  of laboratory tests

 Descriptive summary statistics for the change from baseline to each study visit will be presented by test group, and laboratory test.

Shift tables based on the normal laboratory ranges will also be provided. For the shift tables, the normal laboratory ranges will be used to evaluate whether a particular laboratory test value was normal, low, or high for worst post-baseline relative to the baseline. These summaries will be presented by laboratory test category.

The number and percentage of patients with clinically notable laboratory results after baseline will be presented.

#### **2.7.4 Immunogenicity**

A listing of immunogenicity (anti-VAY736 antibodies) will be provided.

#### **2.7.5 ECG data**

Summary statistics will be presented for ECG variables by visit.

[figure not shown]
#### **2.7.6 Vital signs**

Analysis of the vital sign measurements using summary statistics for the change from baseline for each post-baseline visit will be performed. These descriptive summaries will be presented by vital sign.

The number and percentage of patients with clinically notable vital signs after baseline will be presented.

### **2.8 Pharmacokinetics**

PK data will be analyzed based on the FAS.

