9.1 Analysis sets

The following analysis sets will be used in this trial:

Randomized set (RAN): All patients randomized are included in the Randomized Set. Patients will be analyzed according to the treatment assigned to at randomization. Unless otherwise specified, mis-randomized patients (randomized by mistake in IRT) will be excluded from the randomized set. The RAN will be used for summaries of patient disposition and analysis sets.

Mis-randomized patients are defined as those patients who were mistakenly randomized into the IVR prior to the site confirming all eligibility criteria had been met and to whom no study medication was given. Mis-randomized patients are treated as screen failures.

Full analysis set (FAS): comprises all patients in the RAN to whom study treatment has been assigned. Following the intent-to-treat principle, patients will be analyzed according to the

treatment assigned to at randomization and the stratum at baseline. FAS will be used for all efficacy variables, unless otherwise stated.

Safety set (SS): includes all patients who received at least one dose of study medication. Patient will be analyzed according to treatment received and the stratum at baseline. The safety set will be used in the analysis of all safety variables.

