9.3 Treatments

Study treatment

The analysis of study treatment data will be based on the safety set.

The duration (days) of study medication administration will be summarized. This will be calculated by subtracting the date of the first administration of study medication from the date of last administration and then adding the dosing interval for 28 days. In calculating the duration of treatment, days of temporary interruption of study medication for any reason will be included. Number and percentage of patients being exposed for prespecified time intervals (any, ≤ 3 months, ≤ 6 months, etc. up to ≤ 12 months) as well as cumulative exposure will also be summarized.

Prior and concomitant medication

Prior medications are defined as treatments taken and stopped prior to first dose of study treatment. Any medication given at least once between the day of first dose of randomized study treatment and the date of the last study visit will be a concomitant medication, including those which were started pre-baseline and continued into the period where study treatment is administered.

Prior and concomitant medications will be summarized in separate tables for SAF. Medications will be presented in alphabetical order, by Anatomical Therapeutic Classification (ATC) codes and grouped by anatomical main group. Tables will show the overall number and percentage of patients receiving at least one treatment of a particular ATC code and at least one treatment in a particular anatomical main group.

The number and percentage of patients receiving systemic therapies for pSS as prior and concomitant background medication will be presented separately by preferred term.

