9.5.4 Pharmacokinetics

PK data will be analyzed based on the SAF.

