## **2.2 Analysis sets**

**Enrolled set (ENR):** All subjects who signed the informed consent are included in the Enrolled Set. The enrolled set will be used when screening information needs to be presented.

**Randomized set (RAN):** All patients randomized are included in the Randomized Set. Patients will be analyzed according to the treatment assigned to at randomization. Unless otherwise

specified, mis-randomized patients (randomized in IRT by mistake) will be excluded from the randomized set. The RAN will be used for summaries of patient disposition and analysis sets.

**Full analysis set (FAS):** comprises all patients in the RAN to whom study treatment has been assigned. Following the intent-to-treat principle, patients will be analyzed according to the treatment assigned to at randomization, but actual stratum. FAS will be used for all efficacy variables, unless otherwise stated.

**Per Protocol set (PPS):** includes all FAS patients who are not excluded due to major protocol deviations (see [Section 5.6](#)).

**Safety set (SS):** includes all patients who received at least one dose of study medication. Patient will be analyzed according to treatment received and the actual stratum at baseline. The safety set will be used in the analysis of all safety variables.

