## 4 Change to protocol specified analyses

Not applicable.

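### The SAP analyses PK by assigned arm (FAS), the protocol apparently by treatment received (safety set), and no change is declared

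*SAP*

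**What the plan says.** The two documents name different analysis sets for PK. SAP 2.8 states "PK data will be analyzed based on the FAS". Protocol 9.5.4 states "PK data will be analyzed based on the SAF".

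SAP 2.2 defines the sets:

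- The FAS "comprises all patients in the RAN to whom study treatment has been assigned", and in it "patients will be analyzed according to the treatment assigned to at randomization, but actual stratum".
- The safety set "includes all patients who received at least one dose of study medication. Patient will be analyzed according to treatment received".

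Protocol 9.1 groups the safety set in the same way: "Patient will be analyzed according to treatment received and the stratum at baseline".

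Both documents abbreviate the safety set as SS, and neither defines SAF. The protocol also uses SAF in section 9.3: "Prior and concomitant medications will be summarized in separate tables for SAF". SAP 2.4.2 uses it for the same tables.

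Under changes to protocol-specified analyses, SAP section 4 says "Not applicable".

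**The concern.** A drug concentration reflects what was injected. Grouping by assigned arm protects a randomized efficacy comparison, but it has no such role in describing exposure. If the dose given differs from the dose assigned, the FAS rule files the concentration under a dose the patient did not receive.

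The SAP foresees that case. Deviation TRT02 in SAP 5.5 (Table 5-4) covers patients given the wrong study medication. It removes them only from the per-protocol set, so they stay in the FAS under the assigned arm.

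The PK endpoint (protocol Table 2-1, SAP Table 1-2) concerns exposure at four dose levels. The active doses are 5, 50, 150 and 300 mg, so a misfiled patient can differ from the rest of the arm by a factor of up to 60. What is at stake is the description of exposure by dose, a secondary objective.

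**Working it through.** The documents state no figure on this point, so there is none to reproduce. The check has two parts.

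**1. The two rules side by side**

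| | FAS (SAP 2.8) | Safety set (protocol 9.5.4, reading SAF as SS) |
|---|---|---|
| Entry | treatment assigned | at least one dose taken |
| Grouping | arm assigned at randomization | treatment received |
| Patient given the wrong drug from the start | assigned arm | treatment received |
| Patient never dosed | included | excluded |

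Period 3 adds a difference that needs no dosing error. Under protocol 5.3, patients on placebo in period 2 move to 150 mg without a further randomization, so 150 mg is not an arm that anyone is randomized to. Read literally, FAS grouping files their period 3 concentrations under placebo. Patients on 300 mg are re-randomized 1:1 to 300 mg or placebo. If only the baseline assignment counts, those two groups are pooled.

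The 72-hour sample after the week 48 dose, meant to assess peak concentrations (protocol 6.6.5), is taken only in patients who entered period 3, so it falls entirely in this part of the study.

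Elsewhere the SAP keeps these groups apart. SAP 2.4.1 gives exposure on the safety set with a separate 150 mg row. The long-term scheme in SAP 2.1.1 separates 150 mg, 300 mg for 24 weeks and 300 mg for 52 weeks.

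**2. Scale of one misfiled patient in period 2**

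Inputs:

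- about 45 patients per arm (protocol 3.1, SAP 1.1);
- period 2 doses of 5, 50 and 300 mg (same sections);
- exposure proportional to dose, which is an assumption and is not in the documents;
- the wrong dose given throughout, also an assumption.

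With one of 45 patients assigned dose d1 but given d2:

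- ratio of arithmetic means = (44 × d1 + d2) / (45 × d1)
- ratio of geometric means = (d2/d1)^(1/45)

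| Assigned | Given | Arithmetic mean | Geometric mean |
|---|---|---|---|
| 5 mg | 300 mg | (220 + 300)/225 = 2.31 | 60^(1/45) = 1.10 |
| 5 mg | 50 mg | (220 + 50)/225 = 1.20 | 10^(1/45) = 1.05 |
| 300 mg | 5 mg | (13,200 + 5)/13,500 = 0.98 | (1/60)^(1/45) = 0.91 |

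With no dosing error in period 2, every dosed patient falls in the same group under both rules, and the period 2 concentration summaries agree.

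**The case against.** The strongest reply is that little may turn on this. Trained personnel give every dose and compliance is expected to be high (protocol 6.3), PK is a secondary objective, and the number of dosing errors is unknown. SAP 2.1 also reports the median, quartiles, minimum and maximum. One outlier in 45 barely moves the median and is visible in the maximum. All of this stands and limits the weight of the point. It does not reconcile two unqualified sentences that name different sets.

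A reader might also infer more than the documents support:

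- **That untreated patients in the FAS distort the concentrations.** A never-dosed patient has no post-dose concentration and mainly adds to a denominator. The grouping rule is what matters.
- **That a dilution slip could produce the 2.31-fold shift.** Under protocol 5.5.4 the 5 mg dose is prepared from one vial, from which 1.0 mL (150 mg) can be withdrawn; 300 mg needs a second vial dispensed by IRT. A failed dilution therefore tops out near 150 mg: (220 + 150)/225 = 1.64. Reaching 300 mg takes a dispensing error, and the calculation has it persist throughout.
- **That an exposure-response analysis is compromised.** Neither document visibly contains one.
- **That the SAP moved away from the protocol.** The SAP's document history does not list section 2.8 among the sections changed in either 2019 revision. The texts show a mismatch but not which document changed.
- **That replacing FAS with safety set is enough.** The short-term scheme in SAP 2.1.1 groups by the treatment first received. On that rule, a patient who starts correctly and is misdosed later stays in the original group within the safety set too.

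Text near SAP 2.8 is redacted and may hold further PK rules, including for period 3. The visible sentence names the FAS without exception.

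**Conclusion.** The point holds as an undeclared inconsistency between the two documents, and the SAP's side of it suits PK less well. Confidence is high on the mismatch, subject to reading SAF as the safety set.

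The size of the effect is conditional. In period 2 it is nil without dosing errors. One patient in the 5 mg arm given 300 mg throughout shifts that arm's arithmetic mean 2.31-fold and its geometric mean 1.10-fold, assuming dose proportionality and 45 patients per arm. The 2.31 is an unfavourable case on the most sensitive statistic, not an expected error. In period 3 a literal reading of the FAS rule does not give 150 mg a group of its own, even with perfect dosing. The primary efficacy analysis is unaffected, so correcting this is desirable but not critical.

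**What to change.** Change SAP 2.8 to the safety set, with concentrations grouped by treatment actually received in each period. 150 mg, 300 mg continued and 300 mg switched to placebo are then shown separately, consistent with SAP 2.1.1 and 2.4.1. State how a patient misdosed at only some visits is handled, since the safety set definition does not settle it. Use one label for the safety set: replace SAF with SS, or define SAF, in protocol 9.3 and 9.5.4 and in SAP 2.4.2.

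If the FAS is intended for PK, declare and justify it in SAP section 4.

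The cost is a few lines of text and some table specification. No new data are needed, because every administered dose is already recorded in the eCRF (protocol 6.3).

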## **2.15 Interim analysis**

An interim analysis will be performed prior to the primary efficacy analysis in addition to regularly scheduled safety reviews of data performed by the DMC.

This interim analysis will occur when at least 100 of the randomized patients (~55% and ~25 per treatment group) will have reached the primary efficacy timepoint at week 24.

Further details of the interim analysis will be provided in a separate SAP.

## **Primary efficacy analysis after all patients finished week 24**

The primary efficacy analysis will be conducted when all randomized patients have finished period 2 (24 weeks of treatment). At this point the primary efficacy analysis and key secondary analyses will be conducted to allow planning activities for upcoming studies.

## 4 Change to protocol specified analyses

Not applicable.

## 5 Appendix

### 5.1 Visit Windows

When visit windows are used, all visits will be re-aligned, i.e., they will be mapped into one of the visit windows. E.g., if the *Week 4* visit of a subject is delayed and occurs on Day 46 instead of on Day 28, say, it will be re-aligned to visit window *Week 8*. In the case of major deviations from the visit schedule, or due to unscheduled visits, several assessments of a subject may fall in a particular visit window (either scheduled or unscheduled).

The following rules are used to determine the window for an applicable visit post baseline: “Lower limit” = “upper limit of prior applicable visit” + 1. “Upper limit” = “target day of current visit” + integer part of (“target day of next applicable visit” – “target day of current visit”)/2. Lower limit of the first applicable visit is always Day 2.

The mapping described in [Table 5-1](#) applies to all visits (not just scheduled visits). Repeat and/or unscheduled visits (which will be numbered in the database according to NCDS standards) will be mapped for analysis purposes in the same way as scheduled visits. This leaves the possibility, then, for multiple measurements within an analysis window. The conventions in [Table 5-2](#) will be used to determine the appropriate measurement to be summarized in the event of multiple measurements within a visit window.

**Table 5-1 Analysis Visit Windows**

Period	Analysis Visit	Target Day	Visit Window for MMRM analysis	Visit Window for by-visit summary
	Baseline	1	≤ 1*	≤ 1*
2	Week 4	28	2-42	2-42
	Week 8	56	43-70	43-70
	Week 12	84	71-98	71-98

	Week 16	112	99-126	99-126
	Week 20	140	127-154	127-154
	Week 24	168	155-W24DT* if patient was dosed on Week 24 155-182 otherwise	
3	Week 28	196		[W24DT**+1]-210 if patient was dosed on Week 24 183-210 otherwise
	Week 32	224		211-238
	Week 36	252		239-266
	Week 40	280		267-294
	Week 44	308		295-322
	Week 48	336		323-350
	Week 52	364		351-378
4	FU Week 4			CRF visit
	FU Week 8			CRF visit
	FU Week 12			CRF visit
	FU Week 16			CRF visit
	FU Week 24			CRF visit
	FU Week 32			CRF visit
	FU Week 44			CRF visit
	FU Week 56			CRF visit
	FU Week 80			CRF visit
	FU Week 104			CRF visit

\* W24DT is the date of week 24 dose

MMRM analysis: ESSDAI, PhGA, ESSPRI, FACIT-F, SF-36, PaGA, salivary flow, [REDACTED]

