- 50 mg dose arm (period 2): The unblinded pharmacist will make the necessary dilution of the solution for s.c. injection as detailed in the pharmacist's manual. The patient will receive one injection of the diluted solution for s.c. injection and one injection of generic placebo.
- 150 mg dose arm (period 3): No dilutions are necessary for this dose level. The patient will receive 1 mL of solution for injection (as after reconstitution) and another injection of generic placebo.
- 300 mg dose arm (period 2 and period 3): IRT will dispense two vials of VAY736 powder for solution. The powder will be reconstituted and the patient will receive two injections of 1 mL each, 150 mg/mL VAY736 solution for s.c. injection.

Generic placebo:

Liquid placebo [REDACTED], for s.c. injections.

Please refer to the pharmacist's manual for further instructions on reconstitution and dilution of VAY736.

Please see [Table 6-1](#) and [6-2](#) for scheduling of IRT contact and administration of study medication and pre-medication. Doses will be administered once every four weeks for 24 weeks in period 2 and once every four weeks for 28 weeks in period 3. The last doses administered in period 2 and 3 will occur on study scheduled visit 106 and 207, respectively.

For the first administration for all patients in period 2 and 3, the patient must remain at the study center for observation for at least 6 hours or longer as per local requirements.

[REDACTED]

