5.6.5 Early study termination by the sponsor

[figure not shown]
The study can be terminated by Novartis at any time for any reason. This may include reasons related to the benefit risk assessment of participating in the study, practical reasons, or for regulatory or medical reasons (including slow enrollment). Should this be necessary, the patient must be seen as soon as possible and treated as a prematurely withdrawn patient. The investigator may be informed of additional procedures to be followed in order to ensure that adequate consideration is given to the protection of the patient's interests. The investigator will be responsible for informing the Institutional Review Board/Independent Ethics Committee (IRBs/IECs) of the early termination of the trial.

6 Visit schedule and assessments

Table 6-1 lists all of the assessments and indicates with an "x" when the assessments are performed and should be documented in the eCRF. Assessments indicated with an "S" will only be documented at source.

Patients must be seen for all visits on the designated day, or as close to it as possible. Missed or rescheduled visits should not lead to automatic discontinuation. Patients who prematurely discontinue the study for any reason should be scheduled for a visit as soon as possible, at which time all of the assessments listed for the final visit will be performed. At this final visit, all dispensed investigational product should be reconciled and the adverse event and concomitant medications reconciled on the CRF.

In period 4, patients will have visits every four weeks for the mandatory 20-week safety follow-up period.

Patients who are not willing to return to the site for follow up visits in period 4, will be contacted for safety evaluations during the 30 days following the last administration of study treatment.

Table 6-1 Assessment schedule for period 1 (Screening) and period 2 (Randomized treatment period)

Period	Period 1: Screen	Period 2: Treatment					Notes
Visit	1 101 (BL)	102	103	104	105	106	199 / TD ⁷
Day	-28 1	28	56	84	112	140	168
Week	-4 0	4	8	12	16	20	24
Obtain informed consent (IC)	x						IC obtained prior to all study specific screening procedures
Demography	x						
Inclusion/exclusion	x	x					
Medical history	x						
Physical exam	S	S	S	S	S	S	
Height ¹ , weight, vital signs	x	x	x	x	x	x	1Height only collected at Screening
PhGA of overall disease activity	x	x	x	x	x	x	
ESSDAI	x	x	x	x	x	x	
Salivary flow, stimulated	x	x		x		x	

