Urine pregnancy ¹⁴	x x	x x	x x	x x
Serum pregnancy				x
Urinalysis	x x	x x	x x	x x
Lipid ⁸				x ⁸ Lipid is collected from same sample as chemistry
PK sample	x x	x x	x x	x* [*] Only for patients who prematurely withdraw

Period 4: Follow-up	Mandatory follow-up visits			Conditional individualized follow-up visits			Mandatory	Notes
Visit	301	302	303 ⁹	304	305 and 306	307, 308 and 309	399 ¹⁰ /PSD/ (EoS)	
Study week for patients who completed period 3 treatment	56	60	64	68	76 and 84	96, 108¹² and 132	156 ¹¹	¹² Marks the 1 year follow up time point
Study week for patients who completed period 2 treatment	28	32	36	40	48 and 56	68, 80¹² and 104	128 ¹¹	¹² Marks the 1 year follow up time point
Immunogenicity			x		x		x	

PSD = Premature subject/patient discontinuation; X = assessment to be recorded on clinical data base; S = assessment to be recorded on source documentation only

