6.6.5 Pharmacokinetics

At each visit indicated, a blood sample will be taken prior to dosing by either direct venipuncture or an indwelling cannula inserted in a forearm vein. Further details on sample collection, numbering, processing and shipment can be found in the Laboratory Manual.

For all patients who entered period 3, an additional sample will be taken 72 hours post last dose of study treatment received (72 hours after week 48 dosing). This sample will be used to assess peak concentrations. All patients entering period 3 must return to the site for sample collection.

The detailed method description to assess VAY736 concentrations will be described in the bioanalytical raw data of the study and in the respective Bioanalytical Data Report (BDR).

7 Safety monitoring

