### 1.1 Study design

This is a randomized, double-blind, placebo-controlled, multicenter, parallel-group trial in approximately 180 patients with active pSS. The study is divided into 4 study periods:

**Period 1:** A screening period of 4 weeks to assess patient eligibility. Patients can be re-screened only once and no study-related re-screening procedure should be performed prior to written re-consent by the patient.

**Period 2:** At baseline, eligible patients will be randomized to one of three VAY736 dose arms (VAY736 5 mg, 50 mg or 300 mg s.c.) or a placebo arm. Blinded study drug will be administered every four weeks for a 24-week period. Approximately 45 patients will be randomized per treatment group. [REDACTED], randomization will be stratified by:

- baseline ESSDAI score (<10 or  $\geq 10$  based on weighted scores)

[REDACTED]

The primary endpoint will be assessed at the end of period 2 (week 24).

[figure not shown]
Treatment assignment in period 2 will remain double blinded until the end of period 3.

**Period 3:** After week 24 assessments, patients in the VAY736 300 mg arm will be re-randomized in a 1:1 ratio to either continue VAY736 300 mg s.c. every four weeks or switch to [REDACTED] placebo up to week 52. Patients who received placebo during period 2 will be switched to VAY736 150 mg s.c every four weeks up to week 52. Patients who received 5 mg and 50 mg s.c. in period 2 will proceed directly to period 4. Treatment assignment in period 3 will remain double blinded until the end of the study period.

**Period 4:** The safety follow-up period lasts for a minimum of 20 weeks from last dose administration of VAY736, or longer (with reduced visit frequency) [REDACTED] whichever occurs first ([Figure 1-1](#)) ([van Vollenhoven 2012](#); [Emery 2014](#), [Genovese 2008](#)).

Patients who have not yet recovered their B-cell counts two years after last VAY736 dosing, will be discharged from the study and undergo their End of Study (EoS) visit. Patients who will be treated with another immunmodulatory or immunsuppressive treatment (e.g. azathioprine, cyclophosphamide, high dose glucocorticosteroids) after completion of the minimum 20 week safety follow-up period are excluded from further safety follow-up.

The primary efficacy analysis will be performed when all patients have completed the week 24 study visit.

**Figure 1-1** Study design

[figure not shown]

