## 2.1.1 General definitions

### Study treatment

The following grouping scheme / data selection will be used for reporting of safety summary:

Grouping Scheme 1 (short term summary, up to 24 weeks): only data on or before the end of treatment (defined below) in period 2 will be tabulated. The treatment used will be according to the treatment groups initially received:

Placebo  
VAY736 5 mg  
VAY736 50 mg  
VAY736 300 mg  
Any VAY736

Grouping Scheme 2 (long term summary, all study periods):

VAY736 5 mg  
VAY736 50 mg  
VAY736 150 mg  
VAY736 300 mg 24 Weeks (this group includes patients receiving VAY736 300 mg and stopping treatment in period 2, as well as those receiving placebo in period 3)  
VAY736 300 mg 52 Weeks  
Any VAY736 300 mg  
Any VAY736

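### Period 4 laboratory summaries follow the CRF visit label, so pooled 300 mg columns mix patients 8 and 36 weeks after their last VAY736 dose

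*SAP*

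**What the plan says.** In SAP Table 5-1 the column "Visit Window for by-visit summary" gives day ranges for periods 2 and 3. All ten period 4 rows, FU Week 4 to FU Week 104, refer only to the CRF visit, with no target day and no window. SAP 2.1.1 (Period) starts period 4 on the day after treatment ends in period 2 or 3. Blinded placebo in period 3 counts as treatment for this purpose.

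The length of follow-up uses another clock. SAP 1.1 counts the 20-week minimum from the last VAY736 dose, and its discharge rule concerns "Patients who have not yet recovered their B-cell counts two years after last VAY736 dosing".

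Grouping Scheme 2 in SAP 2.1.1 covers safety summaries over all study periods. It has three 300 mg columns:
- a 24-week column, which combines patients who stopped in period 2 with those who received placebo in period 3;
- a 52-week column for continuers;
- a total, "Any VAY736 300 mg".

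There is also a total over all VAY736 doses. For laboratory data, SAP 2.7.3 states: "Descriptive summary statistics for the change from baseline to each study visit will be presented by test group, and laboratory test". Protocol Table 6-3 schedules hematology, IgG and IgM throughout period 4.

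**The concern.** Period 4 follows patients after treatment has ended. A mean at a follow-up visit is easy to read as the state of patients a known time after their last active dose. For patients re-randomised from 300 mg to placebo the label does not measure that, because 28 weeks of placebo visits come between their last scheduled VAY736 dose and the point where the continuers' last dose falls. If they share a column with continuers or with period 2 stoppers, a mean of IgG, IgM or neutrophils at a given FU week describes no single washout time. This matters most for the highest dose, where a reader would look for persistence and recovery of laboratory effects.

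The SAP already treats these patients as off drug elsewhere: SAP 2.4.1 ends their exposure at the period 2 end of treatment. That logic is not carried into the follow-up axis.

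**Working it through.** **Inputs**
- Last-dose visits (Protocol 5.5.4): "The last doses administered in period 2 and 3 will occur on study scheduled visit 106 and 207, respectively".
- Visit 106 is week 20 (Protocol Table 6-1). Visit 207 is week 48 (Protocol Table 6-2, and Protocol 6.6.5: "72 hours after week 48 dosing").
- Period 4 visit weeks (Protocol Table 6-3). The row "Study week for patients who completed period 3 treatment" gives 56, 60, 64, 68, 76, 84, 96, 108, 132, 156. The row for period 2 completers gives 28, 32, 36, 40, 48, 56, 68, 80, 104, 128.
- About 45 patients per arm, and a 1:1 split of the 300 mg arm at week 24 (SAP 1.1).

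**Step 1: reproduce the SAP labels.** FU label = study week minus the week the treatment period ended. After period 3: 56 − 52 = 4, 60 − 52 = 8, and so on to 156 − 52 = 104. After period 2: 28 − 24 = 4, and so on to 128 − 24 = 104. All ten labels match in both rows, so they count from the end of the treatment period.

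**Step 2: time since the last VAY736 dose.** This is study week minus 48 for continuers, and study week minus 20 for switchers to placebo.

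| FU label | Study week | Continuers | Switchers |
|---|---|---|---|
| 4 | 56 | 8 | 36 |
| 16 | 68 | 20 | 48 |
| 32 | 84 | 36 | 64 |
| 56 | 108 | 60 | 88 |

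The gap is 48 − 20 = 28 weeks in each row.

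**Step 3: how far the gap extends.** Two years after a week 20 dose is 20 + 104 = study week 124. FU Week 56 (week 108) falls before this. FU Week 80 (week 132) and FU Week 104 (week 156) fall after it, so the discharge rule may remove switchers from those rows.

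**Step 4: share of each column, if every patient is re-randomised and retained.**
- 300 mg total: 45 / 2 is about 22 continuers and 22 switchers. Mean time since last dose at FU Week 4 is (8 + 36) / 2 = 22 weeks, a time at which no scheduled completer stands.
- All-doses total: about 22 of 4 × 45 = 180, or 12%. On schedule the other groups stand at 8 weeks (5 mg and 50 mg: 28 − 20; 150 mg: 56 − 48).

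**Step 5: the 24-week 300 mg column.** Switchers are at 36 weeks at FU Week 4. A period 2 stopper's time depends on the route taken:
- Straight into period 4 after the discontinuation visit (note 7 to Protocol Table 6-1): taking SAP end of treatment as last dose plus 27 days, and the first follow-up visit as 28 days later, 27 + 28 = 55 days, or about 8 weeks.
- Scheduled visits to week 24 first, as Protocol 5.6.2 asks: 28 − 16 = 12 weeks to 28 − 0 = 28 weeks, for last doses at weeks 16 to 0.

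The documents do not say how many such patients are expected.

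**The case against.** The case against the point is strong on reach, and much of it stands.

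- **Separate columns exist.** A reader might infer that every 300 mg column mixes washout times. It does not: the 52-week column is separate and clean for scheduled completers, and continuers meet switchers only in the two totals. This stands. The 24-week column still mixes switchers with stoppers.
- **Early washout is tabulated.** Switchers' weeks 28 to 52, which are 8 to 32 weeks after the week 20 dose, appear in the period 3 rows. That is true, but continuers' early washout sits in the follow-up rows, so the two are never aligned.
- **No contradiction.** The SAP sets the start of period 4 by end of treatment and its minimum length by last VAY736 dose. The FU labels agree with Protocol Table 6-3. This is a choice of axis, not an inconsistency.
- **Not every visit.** A reader might carry the 28-week gap to FU Week 104. The two-year discharge rule prevents that for FU Weeks 80 and 104.
- **Direction is not shown.** A reader might infer that pooling makes recovery look faster. That would need an effect that wanes steadily. The visible text gives no half-life or recovery data, later visits are conditional, and the 52-week group had longer exposure.
- **Other outputs.** Immunogenicity is only listed (SAP 2.7.4), no by-visit PK summary is visible (SAP 2.8), and shift tables use the worst post-baseline value. These are not affected by the FU label.
- **Redactions.** Blacked-out SAP sections may contain a recovery analysis by time since dose. This cannot be checked.

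**Conclusion.** The point holds as a limited one about descriptive safety tables. Followed as written, the visible plan produces period 4 by-visit laboratory means, including IgG, IgM and neutrophils, that match no defined time off drug in three columns: the 300 mg total (up to about half switchers), the 24-week 300 mg column (mix unknown) and, with less dilution, the all-doses total (about 12% switchers). At FU Week 4 the contrast is 8 against 36 weeks, and the 28-week gap holds through FU Week 56.

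The week counts assume that doses and visits occur on schedule. The shares assume about 45 patients in the arm, all re-randomised and equally retained. Counting from the next due dose instead of the last injection gives 4 against 32 weeks, with the same gap. The week 24 primary analysis is untouched. The change is worth making because it is cheap and concerns the highest-dose arm.

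**What to change.** In SAP 5.1 and Table 5-1, add a second time axis for period 4 by-visit summaries of laboratory values and IgG/IgM: weeks since the last VAY736 dose. Compute it from recorded dose dates, with windows around the planned 8, 12, 16 and 20 weeks and onward. Put the period 3 data of 300 mg-to-placebo patients on the same axis.

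Keep the CRF-visit tables by regimen, since they allow the two re-randomised groups to be compared at the same study week. In those tables give 300 mg-to-placebo patients their own column, as SAP 2.3.1 already does for period 4 disposition, and do not pool FU visits across the 300 mg subgroups. State which route into period 4 applies to early stoppers, since Protocol 5.6.2 and the note to Protocol Table 6-1 need to be reconciled.

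The cost is SAP wording, re-windowing of data already collected, some extra tables and uneven numbers per window. No new data collection is needed.
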